9.0. RANDOMIZATION & STUDY DRUG ADMINISTRATION

9.1. Randomization: After initial assessments, participants are randomized to double-blinded Phase 1 drug assignment (escitalopram or placebo). As our primary interest for Phase 1 is related to escitalopram response, we will allocate participants in a 2:1 drug-to-placebo ratio. Randomization will be conducted by the Vanderbilt Investigational Drug Service. Nondepressed individuals will not be randomized to study drug.

Randomization will be stratified by MRI measures of total cerebral WML volume. Our measurement of total WML volume is automated and available within 24 hours of the scan and subjects will be stratified as "high" or "low" total cerebral WML volume. Based on pilot data, we will use a cutoff of 3.86mL; this is the median 3T WML volume from a cohort of 145 depressed elders analyzed using our WML segmentation method. When we reach 50% enrollment, we will re-assess this cutoff based on study data and adjust if necessary.

If there are delays in scan processing, stratification will be determined using the Coffey-modified Fazekas visual rating scale (2), dichotomizing participants as "high" (2 or 3, confluence of foci) or "low" (0 or 1, absent or punctate foci).

MRI measures will only be used for stratification. They will not guide or determine treatment decisions.

9.2. Phase 1: Blinded Escitalopram or Placebo: We selected escitalopram due to its tolerability, ease of dosing, and lack of effects on dopamine and norepinephrine (115). The Vanderbilt IDS will prepare over-encapsulated escitalopram and matching placebo and maintain the blinded assignment in case of emergencies. Participants will receive one tablet (10mg or placebo) for at least 2 weeks. If tolerated, it can be increased to a target dose of two tablets (20mg) daily at the two-week study contact, but dosing changes will not be made at week 6 or later. For problems with tolerability, the dose can be reduced to the previous level, but not below one tablet daily.

9.3. Transition: After 8 weeks subjects will be assessed for remission (MADRS \leq 7). Those achieving remission will end their study participation. Those who are not remitted will have their Phase 1 drug tapered over a week to decrease the chance of discontinuation syndrome then progress to Phase 2.

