We will use a similar approach for Exploratory Aim 1, where we examine how cognitive test performance may serve as a marker of WML tract damage. Including the previous covariates plus education, cognitive test results will be on the independent side with tract WML values on the dependent side.

Data from nondepressed elders will be integrated into the above analyses. We will test for group differences in the neuroimaging and cognitive measures described above. We will also include a group variable (depressed or not depressed) in analyses.

Aim 2 examines how tract measures predict remission. Following our previous approach (21), our definition of remission is MADRS ≤ 7 . Secondly, we will examine drug response (50% improvement on MADRS). Remission / response status for subjects with missing data will be estimated via multiple imputation

method assuming that dropouts are missing at random.

We will use two regression models to test for mediation while adjusting for baseline MADRS, age, sex, and vascular risk. To assess indirect effects of tract WML and FC measures as mediator variables, we will regress a potential mediator on a tract-based measure (an explanatory variable of interest). We will fit another model in which antidepressant remission or nonremission serves as outcome variable, and the potential mediator and tract-derived measure serve as covariates. The second model can be either logistic or linear regression model depending on the nature of outcome. The product of two beta coefficients corresponding to the tract-based measure in the first model and to the mediation variable in the second model will be assessed by constructing bootstrapped 95% confidence intervals (CI); statistically significant difference from zero implies that the relationship between the outcome and explanatory variable is mediated by the variable in question (127,128).

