This approach will slightly differ for each study phase. For Phase 1, models will include drug arm (placebo or escitalopram). To examine for differences in how tract impairment affects remission in each arm, we will test for interactions between drug assignment and tract integrity (WML & FC). We will explore significant interactions in individual models. For subjects entering Phase 2, we will test for differences in tract integrity (WML & FC) between those originally assigned to escitalopram and placebo. If differences are observed, in models we will control for original Phase 1 cohort assignment. In exploratory models, we will use similar approaches to test for the additional effect of cognitive domain function (Table 5) on remission. We will also use this approach for Exploratory Aim 2 when we examine the effect of connectivity deficits in other tracts.

Importantly, the relationship between connectivity and antidepressant response may not be linear. It is possible that a ‘threshold’ must be crossed in order for tract connectivity deficits to influence response (3). To properly take into account nonlinear effect of a continuous predictor variable (e.g., WML, FC) on response variable (e.g., remission or nonremission) in the models, we will employ restricted cubic splines of the predictor. Statistical significance of the nonlinear terms via F-test implies that the relationship between the two measures of interest can be nonlinear.

15.1. Sample Size and Statistical Power:

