Aim 1: From our published report (129) correlations of the FC of the PFC with the amygdala and the hippocampus were in the range of 0.52 to 0.55. A sample of 130 subjects, will have > 90% statistical power for associations ≥ 0.30 (two-tailed $\alpha = 0.05$). However, our primary approach to the analysis of Aim 1 will use canonical correlation with no known powering algorithms; sample size and effect estimates are used to guide the appropriateness. Using the multiple regression approach (single dependent) as a conservative estimate, a sample size of 130 achieves 83% statistical power to detect an R^2 as small as 0.06 (standardized beta = 0.20, 6% shared variance) attributed to the association of WML with a significance level (alpha) of 0.05 after adjusting for other proposed covariates. These calculations assume that the variables for which we are adjusting have an R^2 of 0.10 (10%) (130). We suspect that the control variables will have a higher inter-correlation value, thus increasing our power for testing the effect of a single variable.

Aim 2: The study includes a placebo arm to identify effects specific to an active depressant while having a comparable number of subjects receiving each active drug. Powering the study for Phase 1, Table 2 presents estimates for our proposed sample size using unadjusted effects of low vs. high WML values on the respective

outcomes of interest found in our preliminary data. The logistic regression approach allows for the testing of effects adjusted for known covariates. Using this approach, assuming a base non-remittance rate of 0.36 (36%), a sample size of 130 will enable us to detect a log hazard ratio as small as 0.45 for a specific measure. We conservatively included an assumption that covariates would account to up to 10% share of the effect on nonremission. If that value is less, our statistical power will increase for the same hazard ratio. Using high vs. low tract WML volume as an example, after controlling for other effects, our sample will enable us to detect an effect on the likelihood of non-remittance of at least 25% (high WML vs. low WML, $0.45 / 0.36 = 1.25$ or 25% increase). Continuous as well as nonlinear operationalization of effects will be examined.

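### Aim 2 plans ordinary logistic regression in subsets that may hold only 43 to 47 people, where slopes are inflated by about 25-40% on average and some bootstrap refits have no finite estimate; Firth estimation is a cheap improvement

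*Combined protocol and SAP*

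**What the plan says.** Section 15.0 tests mediation for Aim 2 with two regressions. The first regresses the mediator on a tract measure. The second has remission as its outcome, with the mediator and the tract measure as predictors, adjusted for baseline MADRS, age, sex and vascular risk. On the second model the plan says: "The second model can be either logistic or linear regression model depending on the nature of outcome". The product of the two relevant coefficients "will be assessed by constructing bootstrapped 95% confidence intervals (CI"), and mediation is declared when that interval excludes zero. Missing remission or response status is multiply imputed.

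The Phase 1 model takes both arms together and tests arm-by-tract interactions; single-arm models follow only where an interaction is significant. Phase 2 models use the people who go on to bupropion. Phase 1 arm is added if tract integrity differs between the original arms. In a separate paragraph, to allow for a threshold in WML or FC, "we will employ restricted cubic splines of the predictor", with the nonlinear terms judged by an F-test.

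The plan gives no penalty or other small-sample correction, no number of knots, no type or number of bootstrap resamples, and no rule for a resample whose fit does not converge.

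**The concern.** Maximum-likelihood logistic slopes are biased away from zero when there are few events per slope, and the bias grows quickly below about five. Resampling with replacement makes it worse: some resamples separate remitters from nonremitters perfectly, and then no finite estimate exists. Software may drop such a resample or keep a very large coefficient, and the two choices give different intervals.

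Hypothesis 4 (nonremission to bupropion is predicted by the UF but not the CB) can be tested only in Phase 2. The placebo half of Hypothesis 3 leans on the smaller Phase 1 arm. Inflated slopes there would overstate how strongly a tract predicts nonremission. The mediation verdict would depend partly on an unstated software default.

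**Working it through.** **Inputs from the documents**
- Evaluable sample 130 (Section 15.1): "a sample size of 130 will enable us to detect a log hazard ratio as small as 0.45".
- Allocation (Section 9.1): "we will allocate participants in a 2:1 drug-to-placebo ratio".
- Nonremission rate 0.36 (Section 15.1): "assuming a base non-remittance rate of 0.36 (36"%).
- Covariate share 0.10 (Section 15.1): "covariates would account to up to 10% share of the effect on nonremission".
- Alpha, stated for Aim 1 and assumed two-sided for Aim 2: "with a significance level (alpha) of 0.05".
- Six slopes: four covariates, the tract measure and the mediator.

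**The plan's own Aim 2 figure.** Section 15.1 gives no power for its detectable effect of 0.45. Power = Φ(b√I − 1.96).
- Event-count (Cox-type) information: I = 130 × 0.36 × 0.90 = 42.1. Then 0.45 × √42.1 = 2.92, 2.92 − 1.96 = 0.96, and power is 83%.
- Logistic information per SD of the predictor: I = 130 × 0.36 × 0.64 × 0.90 = 27.0. Then 0.45 × √27.0 = 2.34, 2.34 − 1.96 = 0.38, and power is 65%.

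The figure therefore reproduces, at the 83% power stated for Aim 1, only with a hazard-ratio formula. It covers 130 people; no calculation addresses Phase 2 or a single arm.

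**Subset sizes**
- Escitalopram: 130 × 2/3 ≈ 87. Placebo: 130 × 1/3 ≈ 43.
- Phase 2: 130 × 0.36 ≈ 47 if 0.36 is the overall nonremission rate; 130 × 0.64 ≈ 83 if it were 64%; about 87 if bupropion is to match escitalopram in number, as the Section 15.1 rationale implies.

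**Slope inflation.** Simulated data with six slopes, a 36% event rate, true slopes of 0.45 or 0.90 per SD for tract and mediator (opposite signs, correlation −0.3) and modest covariate effects. The row for 130 adds arm and two interactions (nine slopes) and reports the interaction slopes.

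| n | Events | Events per slope | Mean ML inflation | Median |
|---|---|---|---|---|
| 43 | 43 × 0.36 ≈ 15 | 2.6 | 35-40% | 21-27% |
| 47 | 47 × 0.36 ≈ 17 | 2.8 | 26-42% | 17-27% |
| 87 | 87 × 0.36 ≈ 31 | 5.2 | 12-16% | 7-12% |
| 130 | 130 × 0.36 ≈ 47 | 5.2 | 10-13% | 8-11% |

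A separate simulation with a true slope of 0.60 and six slopes agrees. The mean ML estimate is 0.76-0.85 at n = 43-47 (0.76/0.60 = 1.27; 0.85/0.60 = 1.42), 0.69 at n = 87 (15% high) and 0.65 at n = 130 (8% high). At an assumed 20% event rate, mean inflation in the first set-up is 46-49% at n = 43, 41-44% at n = 47 and 17-21% at n = 87.

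**With Firth's penalty** (maximise log L + ½ log|I(β)|): mean inflation is between about −1% and +7% at n = 43, 47 and 87. With true slope 0.60 the mean is 0.60-0.64, and at n = 43-47 the root mean squared error falls from 0.62-0.71 to 0.43-0.44.

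**Bootstrap refits with no finite ML estimate.** Linear terms only, since the plan bootstraps a product of two single coefficients; separation was detected by linear programming.

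| Event rate | n = 43 | n = 47 | n = 83-87 |
|---|---|---|---|
| 36% | 4-16% | 3-12% | 0.1% or less |
| 50% | 3-10% | 2-7% | none seen |

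A 64% rate has the same smaller class as 36% and gave 5-18% at n = 43 and 3-9% at n = 47, which differs little from the 36% row. A further check found essentially no failures at n = 60 or more, and the interaction model in 130 had under 0.1%. An assumed 20% event rate is worse: 17-27% at n = 47, and 0.5-3.5% at n = 87.

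**The case against.** Much of the opposing case stands.

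- The planned Phase 1 test is the interaction in about 130 people, where inflation is modest and refits do not fail. Single-arm models are conditional on a significant interaction and exploratory.
- Forty-seven is not a settled Phase 2 size. Section 15.1 calls 0.36 a base rate, uses it as the low-WML reference, and says that the two active drugs should have similar numbers. Section 14.0 also lets some people move to Phase 2 before completing Phase 1. With about 87 people the problem is mild.
- The hypotheses ask whether a tract predicts nonremission. With a true slope of zero at n = 47, the mean estimate was about zero, Wald tests rejected about 5% of the time and likelihood-ratio tests 7-8%. With a true slope of 0.60, a bias of 0.16-0.20 compares with a sampling SD of 0.55-0.62. Imprecision is the larger limit, and a penalty adds no events.

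A reader might infer that most bootstrap refits would fail in every subset once splines are used. The documents do not support that. The bootstrapped quantity is one product of two coefficients, whereas a splined predictor has several. The splines come in a separate paragraph with their own F-test, and no knot number is given.

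What the objection leaves untouched is that, at 43-47 people, the estimates are materially too large, Firth also cuts their error by about a third, and the interval that decides mediation has no rule for failed refits.

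**Conclusion.** The point holds in limited form, as a cheap improvement. In a placebo-only model, or in Phase 2 if it has about 47 people, ordinary logistic slopes would be inflated by about 25-40% on average (medians about 15-30%), and roughly 2-16% of mediation refits would have no finite estimate. At 87 people inflation is 12-16%; in the full Phase 1 model it is under about 15%. At 60 or more people almost no linear-term refits fail at event rates of 36-64%.

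These are simulation results, not figures in the documents. They rest on assumed true effects (0.45 to 0.90 per SD), an assumed tract-mediator correlation, and assumed Phase 2 remission rates; a smaller outcome class would make both problems worse. The Phase 2 size is uncertain because the statements in Section 15.1 point to different numbers. Nothing here shows that Wald tests reject too often under the null, or that the mediation interval is undefined.

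**What to change.** In Section 15.0:

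1. Specify Firth penalised logistic regression for the Phase 2 and single-arm models of remission and response and, for consistency, for the Phase 1 interaction model.
2. Use the same estimator in every bootstrap refit of the mediation product, so that every resample gives a finite estimate. State the interval type and the number of resamples.
3. State one rule for combining penalised estimates and bootstrap intervals across the multiple imputations.
4. Say how many people are expected in Phase 2, reconciling the 36% rate with the intended balance between the active drugs.

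Splines can stay in Phase 2, where the threshold question also applies; limiting the number of knots there is optional.

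The cost is plan wording, standard software, a little more analysis work (mainly the pooling rule) and slight shrinkage of the estimates. No change to design or data collection is needed.

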Hypothesis 1: Greater CB WML volume is associated with a) reduced resting-state connectivity of frontal, temporal, and cingulate regions and b) deficits in attention, memory and processing speed.

Hypothesis 2: Greater UF WML volume is associated with a) reduced resting state functional connectivity between frontocingulate and medial temporal regions, and b) greater depression severity and negativity bias.

Exploratory Hypothesis: Greater CB WML volume is associated with failure of anterior and posterior DMN nodes to deactivate during attentional components of the fMRI task. Greater UF WML volume is associated with greater medial temporal reactivity during affective components of the fMRI task.

Specific Aim 2: To determine whether deficits in tract structural / functional connectivity predict nonremission to antidepressant treatments and if these relationships vary based on antidepressant mechanism of action.

Hypothesis 3: Nonremission to escitalopram will be predicted by: a) greater WML volume in the CB and UF, and b) reduced resting functional connectivity between structures connected by the CB and UF. Greater WML severity and reduced functional connectivity in these tracts will not significantly predict response to placebo.

Hypothesis 4: Nonremission to bupropion will be predicted by a) greater WML volume in the UF but not CB, and b) reduced resting functional connectivity deficits between structures connected by the UF but not CB.

Exploratory Aims: **Expl. Aim 1)** To determine if specific cognitive measures may serve as markers of focal tract WML damage. **Expl. Aim 2)** To use whole-brain multimodal imaging approaches to examine how connectivity differences in other brain regions may also predict nonremission to antidepressants.

For exploratory analyses, we will also recruit 30 elders with no psychiatric history. Data from this population will help us understand whether our neural and cognitive findings in depression represent differences from what is seen in healthy aging, or whether our observations in depressed elders are within the range of normal aging. This will be important for data interpretation and planning for future projects.

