maladaptive cognitive processes (61,65). In MDD we observe a dissociation between anterior and posterior DMN nodes (66) while within-node functional connectivity is increased (38,46,63,64). As reduced functional connectivity is related to altered CB structure (67,68), we propose that WMLs in the CB adjacent to the cingulate gyrus may disrupt communication between DMN nodes. This would impair anterior-posterior connectivity, resulting in difficulty coordinating deactivation of the DMN during tasks (61). This contributes to deficits in **attention** (69,70) and **processing speed** (59,71-73), deficits associated with poor antidepressant response (21,57). *Additionally*, damage to the CB in the region of the hippocampus may have further effects. WMLs in this region may disrupt hippocampus-posterior cingulate connectivity (31,47,74) resulting in poorer episodic memory performance (75-77). This results in **episodic memory deficits** that are also associated with poor LLD antidepressant responses (21) (Figure 2.c).

3.4. Antidepressants with different mechanisms of action: Antidepressant treatment changes brain metabolism (78-82). However, antidepressants with different mechanisms of action have different effects on neural circuit connectivity (83,84) or neural activity during tasks (85,86).

The relationship between neural circuit deficits and the antidepressant response may *depend on the drug's specific mechanism of action*. We hypothesize that tract damage predicts nonresponse to antidepressants that affect neurotransmitter systems projecting through that tract. Serotonergic neurons project widely through the CB (87), but also to the orbitofrontal cortex and medial temporal lobe (88-90), suggesting UF involvement. Noradrenergic projections largely overlap with serotonergic innervation (91), including CB projections (92). In contrast, dopaminergic neurons have discrete pathways (93-96). Dopaminergic mesocortical and mesolimbic fibers may pass through the UF (97), but compared to serotonin or norepinephrine, have less CB projections (98). *Thus drugs affecting serotonin and norepinephrine may require intact connectivity in both the CB and UF, while dopaminergic agents may depend less on the CB.*

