7.0. STUDY OVERVIEW

After consent, subjects will be evaluated for eligibility. After standardized clinical and cognitive assessments and MRI, subjects will begin 8-weeks of double-blinded study drug, either escitalopram or placebo. Those who do not remit, defined as a MADRS ≤ 7 at the last assessment, will enter an 8-week open-label trial of bupropion XL. Subjects will be evaluated every two weeks via monthly clinic visits and telephone visits at

intervening two weeks.

Nondepressed participants will only complete the screening and baseline assessments. They will not receive study medication or follow-up assessments.

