11.4 Repeat MRI (SUBSTUDY)

As an optional procedure, we will ask randomized depressed participants to have a repeat MRI after completing Study Phase 1 (the 8-week blinded, placebo-controlled escitalopram phase). MRI procedures will be the same as in the baseline assessment. We will ask participants about participating during enrollment however they may change their mind at any point during study participation. This adds no additional risks to the project.

While the purpose of the overall study is to examine how imaging may serve as a predictor of antidepressant response, the overall Aim of the substudy is to examine how neural network connectivity changes during the course of the 8-week trial. We hypothesize we will observe differences between individuals who do and do not remit during Phase 1, wherein individuals who remit will exhibit post-treatment network connectivity similar to nondepressed elders. We will also examine whether there are differences in the interval change between individuals who remit on active drug and those who remit on placebo.

Data on never-depressed elders will be drawn from a separate study (IRB 130360, Frontal Hypoperfusion Effects on Antidepressant Outcomes in Late-Life Depression, PI: [name]). We anticipate that results from this substudy will inform the application for this project's competitive renewal.

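### Phase 1 arm enters the bupropion models only if a pre-test finds arm differences in tract measures; that test has low power and cannot detect the effects of prior treatment

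*Combined protocol and SAP*

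**What the plan says.** Hypothesis 4 (section 2.0) holds that bupropion nonremission is predicted by uncinate fasciculus (UF) lesion volume and, in part b, by "reduced resting functional connectivity deficits between structures connected by the UF but not CB".

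The scan that everyone has comes first. Section 7.0 states: "After standardized clinical and cognitive assessments and MRI, subjects will begin 8-weeks of double-blinded study drug, either escitalopram or placebo". Section 9.1 confirms the order: "Randomization will be stratified by MRI measures of total cerebral WML volume". At week 8, under section 9.3, "Those who are not remitted will have their Phase 1 drug tapered over a week", and they then go on to bupropion. Section 14.0 also lets participants with worsening depression or intolerable adverse events move to Phase 2 during Phase 1.

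For the Phase 2 analysis, section 15.0 says that "we will test for differences in tract integrity (WML & FC) between those originally assigned to escitalopram and placebo". Phase 1 assignment is controlled for only if such differences appear. The section does not say which scan supplies the values, or what counts as a difference.

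Section 11.4 offers an optional substudy in which participants "have a repeat MRI after completing Study Phase 1". Its aim is to "examine how neural network connectivity changes during the course of the 8-week trial". It is given no role in Hypothesis 4.

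**The concern.** Participants reach bupropion by two routes: after nonremission or early exit on escitalopram, or after the same on placebo. This difference in prior treatment may affect bupropion remission whether or not tract measures are balanced between the groups. The plan lets a test on tract measures decide whether the difference is modelled at all.

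The plan also treats connectivity as something that treatment can alter. Section 3.4 says that "antidepressants with different mechanisms of action have different effects on neural circuit connectivity", and the substudy in section 11.4 exists to measure change over Phase 1. A comparison of baseline values cannot register such a change.

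At stake is the FC coefficient for Hypothesis 4b. If arm is related both to tract FC among Phase 2 entrants and to bupropion remission, and the pre-test misses the imbalance, the coefficient is confounded. If tract FC is balanced but arm still affects remission, leaving arm out of a logistic model pulls the conditional odds ratio for FC towards 1.

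**Working it through.** **1. What the pre-test can and cannot detect.** The table assumes baseline FC. This is an inference: the baseline scan is the only one scheduled for all, and section 11.4 assigns prediction to the main study and change to the substudy.

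| Way in which arm could matter in Phase 2 | Seen by comparing baseline tract measures? |
|---|---|
| Different selection into Phase 2 through nonremission | Yes, given enough power |
| FC change during Phase 1 that differs by arm | No; values were taken before treatment |
| Direct effect of prior escitalopram or placebo on bupropion remission | No; tract measures carry no information on it |

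The first row is an imbalance that the plan itself expects. Hypothesis 3 says that tract lesions and FC predict nonremission on escitalopram but not on placebo. Nonremitters from the two arms should then differ on these measures.

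**2. Power of the pre-test.**
- From the plan: 130 participants and a base nonremission rate of 0.36 (section 15.1); 2:1 allocation (section 9.1).
- Assumed: equal nonremission in both arms, no dropout, a true arm difference of 0.5 SD on one tract measure, and a two-sided t-test at 0.05.
- Arms at entry: 130 × 2/3 ≈ 87 escitalopram and 43 placebo.
- Noncentrality: 0.5 × √(n₁n₂/(n₁+n₂)).

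| Nonremission | Phase 2 entrants | n₁, n₂ | Noncentrality | Power |
|---|---|---|---|---|
| 0.36 (plan) | 130 × 0.36 ≈ 47 | 31, 16 | 0.5 × √(496/47) = 1.62 | 0.36 |
| 0.50 (assumed) | 130 × 0.50 = 65 | 43, 22 | 0.5 × √(946/65) = 1.91 | 0.47 |
| 0.65 (assumed) | 130 × 0.65 ≈ 84 | 56, 28 | 0.5 × √(1568/84) = 2.16 | 0.57 |

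On these assumptions a real half-SD imbalance in a given measure is missed 43% to 64% of the time. Dropout would lower the power further. The plan states no figure for this test, so there is none to reproduce.

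**3. Interval from scan to bupropion.**
- Phase 1 completers: 8 weeks + 1 week of taper = 9 weeks, plus any time from the scan to the first Phase 1 dose. The end of the 8-week bupropion phase comes at 9 + 8 = 17 weeks or later.
- Early movers under section 14.0: less than this. With assumed moves at week 2, 4 or 6, the interval is about 3, 5 or 7 weeks with a one-week taper, or 2, 4 or 6 weeks without. The documents do not say whether early movers are tapered.

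**The case against.** The strongest reply is that baseline prediction is the declared question. Section 11.4 describes the study's overall purpose as imaging as a predictor of response, and the background aims at guiding antidepressant selection. Whether FC measured before any study treatment predicts a later bupropion outcome is a legitimate question, and a fresher scan would answer a different one. This stands. It also stands that baseline values are the right ones for detecting selection through nonremission, which may be all that the arm check was meant to do.

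An arm main effect, moreover, does not repair an FC slope weakened by change since the scan. That is true. The case for always including arm rests on prior treatment and undetected imbalance, not on correcting the age of the scan.

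Four stronger readings are tempting, and the documents do not support them:
- *A Hypothesis 4b result would be uninterpretable.* The documents give no size or direction for FC change in nonremitters. The substudy's expectation of connectivity like that of nondepressed elders concerns remitters, and week-8 remitters do not enter Phase 2.
- *The scan is at least 9 weeks old for everyone.* Section 14.0 allows earlier entry to Phase 2.
- *The plan uses the wrong scan.* Section 15.0 names no scan, and baseline FC is a valid choice.
- *Drug status is confounded with remission in the substudy.* Remitters may continue the drug, but sections 9.5 and 12.0 (items 3d and 5) provide a taper for those who stop. No section plans a scan after bupropion starts. The timing wording leaves a difference in drug status possible but does not establish one.

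**Conclusion.** The conditional adjustment is a real weakness. Whether arm enters the Phase 2 models depends on a test in a reduced sample, with power of roughly 0.36 to 0.57 for an assumed half-SD difference. On baseline scans that test cannot respond to two of the three ways in which arm could matter. The power range rests on equal nonremission in the two arms and no dropout, with nonremission from the plan's 0.36 up to an assumed 0.65.

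The timing of the FC predictor limits interpretation; it does not invalidate the analysis. Hypothesis 4b, tested on baseline FC, concerns prediction from FC before Phase 1, 9 weeks or more before bupropion for completers and less for early movers. The bias or attenuation cannot be computed from the documents. The point concerns FC (4b): the documents give no premise that lesion volume (4a) changes over Phase 1. The repeat-MRI timing is a secondary clarification.

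**What to change.** 1. In section 15.0, include Phase 1 arm in every Phase 2 model and delete the condition that a difference must first be seen. The arm comparison of tract measures can stay as description. Cost: one degree of freedom.
2. In section 15.0, state that the primary Hypothesis 4b predictor is FC from the baseline scan. Add a sensitivity analysis using repeat-scan FC in Phase 2 entrants who have it, restricted to scans taken before the first bupropion dose. Cost: one further analysis of scans already planned. Limit: it covers optional volunteers only, so it will be small and self-selected.
3. As a secondary clarification in section 11.4, schedule the repeat MRI at the end of Phase 1, before taper or bupropion where feasible, and record study-drug status at the scan. Cost: a tighter booking window and one recorded item.
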